3.3 Schedule of activities

Refer to Section [10.4](#) for the schedule of activities.

4 STATISTICAL HYPOTHESES

There are no plans to test statistical hypotheses for this trial.

5 INTERIM ANALYSES AND ANALYSIS SEQUENCE

No formal interim analysis is planned. However, data will be reviewed by the SRC after each cohort (details are provided in the CTP). The main statistical analysis will be performed once all patients have completed treatment and safety follow-up. Preliminary statistical analyses may be performed on selected cohorts once all patients have been enrolled and are DLT evaluable.

6 SAMPLE SIZE DETERMINATION

The sample size for Parts 1A and 1B is driven by the 3+3 trial design and will range from three to six DLT-evaluable patients per cohort, depending on the number of DLTs which may occur. In total, between 6 and 60 DLT-evaluable patients are planned to be enrolled in the Part 1A, and between 6 and 30 DLT-evaluable patients are planned to be enrolled in the Part 1B.

7 ANALYSIS SETS AND SUBGROUPS

7.1 Analysis sets

Enrolled Set

Enrolled set will have the patients with a valid date of informed consent.

Safety Set

The Safety set is defined as all patients who received BNT411 (i.e., at least one dose of BNT411).

DLT Evaluation Set

The DLT evaluation set includes all patients from the Safety set who either have completed the DLT evaluation period (i.e., have been observed for minimum 21 days following the first dose) and meet the minimum exposure criterion (i.e., when the relative dose intensity [RDI] of BNT411 in Cycle 1 is 100%) or have experienced a DLT during the DLT evaluation period (Cycle 1).

Patients who do not experience any DLT during the DLT evaluation period are considered to be evaluable if they have been observed for minimum 21 days following the first dose and are considered to have sufficient safety data to conclude that a DLT did not occur.

Patients who are excluded from the DLT evaluation set will be replaced.

Pharmacokinetic (PK) Full Set

The PK Full set will consist of all patients who receive at least one dose of BNT411 and have at least one quantifiable post-dose PK sample.

Pharmacokinetic (PK) Evaluable Set

The PK Evaluable set will consist of all patients in the PK Full Set with a sufficient number of quantifiable PK samples to reliably estimate one or more PK parameters.

Pharmacodynamic (PD) Set

The PD set is defined as all patients who received IMP (i.e., at least one dose of BNT411) and have at least one valid post-dose PD assessment.

The DLT evaluation set will be used for the evaluation of DLTs in order to assess the MTD and the RP2D. The Safety set will be used for all other safety analyses. The PK Full Set, PK Evaluable Set and PD analysis set will be used for the PK and PD summaries, respectively.

Most patient data listings will be based on the Safety set. The Enrolled set will be used to summarize the patient disposition summary and some patient data listings.

For the screened patients, the summary is not by cohort, the number and percentage of patients having failed screening (reported as screen failure in the electronic Case Report Form [eCRF]) will be presented along with a summary of the primary reason for screening failure.

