#### 4.2.1 Replacement of Patients

Patients will be replaced in the following scenarios:

- Patient is not evaluable for DLTs (only applies to patients who do not experience a DLT).
- Patient was enrolled in the trial but did not receive a dose of BNT411.

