## **Safety Set**

The safety set is defined as all patients who received BNT411 (i.e. at least one dose of BNT411).

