#### 9.4.2 Primary Endpoint(s)

The primary objective of the trial is to assess the safety profile of the regimen based on the following endpoints:

- Occurrence of dose limiting toxicities (DLTs) within a patient during the DLT evaluation period
- Occurrence of treatment-emergent adverse events (TEAE) within a patient including grade ≥3, serious, fatal TEAE by relationship
- Occurrence of dose reduction and discontinuation of BNT411 within a patient due to treatment-emergent adverse events (TEAE)

And to determine the MTD and/or RP2D defined as follows:

- MTD the highest tolerated dose
- RP2D based on integrated evaluation of safety, tolerability, clinical benefit, PK, and pharmacodynamics data, for all dose levels tested.

A treatment emergent AE is defined as any AE with an onset date on or after the first administration of trial treatment (if the AE was absent before the first administration of trial treatment) or worsened after the first administration of trial treatment (if the AE was present before the first administration of trial treatment). AEs with an onset date more than 60 days after the last administration of trial treatment will be considered as treatment emergent only if assessed as related to trial treatment by the investigator. Treatment-emergent AEs will be summarized overall and by treatment arm. The trial treatment includes BNT411, atezolizumab, carboplatin, and etoposide.

AEs will be coded using the most recent version of Medical Dictionary for Regulatory Activities (MedDRA®) coding system to get a System Organ Class (SOC) and Preferred Term (PT) for each AE and graded for severity using NCI CTCAE v5.0.

The number and percentage of patients reporting at least one AE will be summarized by PT nested within SOC for each of the following AE types:

- any AE
- related AE
- Grade >3 AE
- related Grade ≥3 AE
- any SAE
- related SAE
- SAE leading to death
- AE leading to dose reduction
- AE leading to permanent discontinuation of treatment
- DLT.

Moreover, the number and percentage of patients with any AE will be summarized by worst NCI CTCAE grade by PT nested within SOC.

DLTs will be presented in terms of listings presenting the reported term and MedDRA PT and SOC term, its time of onset, duration, and outcome, relationship, NCI CTCAE grade, and seriousness including dose exposure data.

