	Route of administration: 100 mL intravenous infusion.	
Route of administration: 100 mL intravenous infusion.
 
For the purpose of this trial, in the USA and UK, atezolizumab, carboplatin and etoposide are considered as non-investigational medicinal products (NIMPs). However, the individual drugs are considered as IMPs in Spain and Germany at the request of the competent authorities due to their use in combination with BNT411.
 
Name: Atezolizumab Dose: recommended dosage is 1200 mg Schedule: Every 3 weeks Route of administration: IV infusion.
 
Name: Carboplatin Dose: commercially available formulation and at the label-recommended doses Schedule: every 3 weeks until cycle 4 Route of administration: IV infusion.
 
Name: Etoposide: Dose: commercially available formulation and at the label-recommended doses (100 mg/m²)
	Route of administration: intravenous infusion.

	Part 1A	Part 1B	Part 2
		
Schedule: On Day 1 of each cycle, administered over 60 minutes following carboplatin administration. On Day 2 and Day 3 of each cycle, administered intravenously over 60 minutes.
 
Route of administration: IV infusion.
 
For combination with atezolizumab and chemotherapy, the administration will be in the following order:
 
Day 1: Atezolizumab > Carboplatin > Etoposide
 
Day 2: BNT411 > Etoposide
 
Day 3: Etoposide
	
Planned number of patients	
The number of patients for Part 1A is driven by the 3+3 trial designBetween 6 to 60 DLT-evaluable patients are planned to be enrolled in Part 1A.	
The number of patients for Parts 1B is driven by the 3+3 trial designBetween 6 to 30 DLT-evaluable patients are planned to be enrolled in Part 1B.	
This will be implemented through a CTP amendment.
Randomization and blinding	This is a non-randomized, open-label trial		The expansion cohort may be a single-arm cohort or a randomized cohort. This will be documented in a CTP amendment.

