Change from baseline: Unless and otherwise specified, will be calculated as follows:

Change from baseline = post-baseline assessment value – baseline assessment value.

If either the baseline or post-baseline assessment value is missing, the change from baseline is set to missing as well.

For the derivations of PK and PD data, see Section [8.6.1](#) and [8.6.2](#).

Duration (Other than “Trial Treatment Duration” defined in Section [8.5.1](#)) will be calculated as follows:

- Duration = last observation date – first observation date + 1.

For conversion of days to months or years the following rules will be applied:

- 1 month = 30.4375 days
- 1 year = 365.25 days

Trial Day and Treatment Day will be calculated for each trial part (1A and 1B) as follows:

- Trial day:
 - If assessment date < treatment start date then trial day = assessment date – treatment start date
 - If assessment date >= treatment start date then trial day = assessment date – treatment start date + 1
- Treatment Day = treatment date – date of first dose of BNT411 +1

That is, trial day 1 indicates the date of treatment initiation.

For BNT411, it is Cycle 1 Day 1 of Part 1A and Cycle 1 Day 2 of Part 1B. For atezolizumab, carboplatin and etoposide it is Cycle 1 Day 1 of Part 1B.

All trial data will be presented as collected in the eCRF/visit assigned in external data. No windowing of data for the purposes of assigning to a visit will occur.

Unscheduled assessments will be listed only and not included in summaries/analysis.

Handling missing data:

For the purposes of assigning treatment-emergent flag for adverse events (AEs), partial or missing AE dates will be handled as follows (trial treatment date is the earliest date of BNT411 in Part 1A and earliest date of atezolizumab, BNT411, carboplatin and etoposide in Part 1B).

- If the day of the month is missing, the onset day will be set to the first day of the month unless it is the same month and year as trial treatment. In this case, in order to conservatively report the event as treatment-emergent, the onset date will be assumed to be the first date of trial treatment.

- If the onset day and month are both missing, the day and month will be assumed to be January 1, unless the event occurred in the same year as the trial treatment. In this case, the event onset will be coded to the day and month of treatment in order to conservatively report the event as treatment-emergent.

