8.5.2 Adverse events

This section includes the description of the analysis planned for the primary endpoints on this trial.

AEs will be coded using the most recent version of Medical Dictionary for Regulatory Activities (MedDRA®) coding system version 26.0 or higher to get a SOC and PT for each AE and graded for severity using NCI CTCAE v5.0. In case a patient has an AE with missing relationship status, the event will be assumed to be related and associated with the treatment received in the summaries (will be listed as collected in the listings). No imputation for missing NCI-CTC grades will be performed.

A treatment-emergent AE (TEAE) is defined as any AE with an onset date on or after the first administration of trial treatment (BNT411 in part1A and BNT411, atezolizumab, carboplatin, and etoposide in Part 1B) (if the AE was absent before the first administration of trial treatment) or worsened after the first administration of trial treatment (if the AE was present before the first administration of trial treatment). AEs with an onset date more than 60 days after the last administration of trial treatment will be considered as treatment-emergent only if assessed as related to trial treatment (BNT411 for Part 1A and BNT411, atezolizumab, carboplatin, and etoposide for Part 1B) by the investigator.

Treatment-emergent AEs will be summarized by cohort and trial part and total within trial part. In addition, treatment-related TEAEs will be summarized by cohort and trial treatment (BNT411, atezolizumab, carboplatin, and etoposide) within trial part.

Only TEAE data will be summarized for the Safety set for each trial part (Part 1A and Part 1B). Non-TEAEs will be listed only.

Dose-limiting toxicities

In general, a DLT for a drug or other treatment is defined as one or more AEs that prevents an increase of the dose level of that treatment (for details on dose escalation decision rules see Appendix 5).

Serious AEs (SAEs), non-serious grade ≥ 3 AEs and clinically significant abnormal laboratory values grade ≥ 3 will be collected and assessed for DLTs (for each dose level during the first cycle). Common Terminology Criteria for Adverse Events (NCI CTCAE) v.5.0 will be used to grade the intensity of AEs.

More details regarding DLTs can be found in the Section 6.6 of the CTP.

For the additional rules and considerations of MTD and RP2D other than what was already defined in Section 1.1, see Section 4.1.1.2 of the CTP.

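### Part 1B counts TEAEs from the Day 1 drugs, but a patient who never receives BNT411 is left out of every safety summary table

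*SAP*

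**What the plan says.** Both documents define the safety population by exposure to BNT411 alone. SAP 7.1: "The Safety set is defined as all patients who received BNT411 (i.e., at least one dose of BNT411". Protocol 9.3: "The safety set is defined as all patients who received BNT411 (i.e. at least one dose of BNT411".

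The Part 1B schedule gives the other three drugs first. SAP 3.2, Table 3, sets the order as "Day 1: Atezolizumab > Carboplatin > Etoposide", with BNT411 on Day 2. SAP 8.1 confirms the start of treatment: "For BNT411, it is Cycle 1 Day 1 of Part 1A and Cycle 1 Day 2 of Part 1B".

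The adverse event window follows all four drugs. Protocol 9.4.2 says "The trial treatment includes BNT411, atezolizumab, carboplatin, and etoposide", and SAP 8.5.2 defines a TEAE by an "onset date on or after the first administration of trial treatment (BNT411 in part1A and BNT411, atezolizumab, carboplatin, and etoposide in Part 1B".

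SAP 8.5 bases all safety analyses on the Safety set. SAP 8.5.1 does the same for exposure to each of the four drugs, SAP 8.5.2 for TEAE summaries, and SAP 8.2 for discontinuation of each drug and the number of deaths. Protocol 4.2.1 lists among the reasons for replacement: "Patient was enrolled in the trial but did not receive a dose of BNT411".

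**The concern.** Protocol 9.4.2 states: "The primary objective of the trial is to assess the safety profile of the regimen". In Part 1B the regimen is four drugs, and the plan opens the event window on Day 1 when three of them are given. It then counts events in that window only for patients who later receive at least one dose of the fourth. Membership of the safety population can therefore depend on what happened after treatment began.

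If a Day 1 reaction is severe enough that BNT411 is never given, the patient leaves both the numerator and the denominator of the primary safety summaries. That includes the summaries of events related to atezolizumab, carboplatin or etoposide, drugs which the patient did receive. With cohorts of 3 to 6, one such patient can visibly change a reported rate.

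**Working it through.** The plan states no figure to reproduce here, so the check follows one Part 1B patient through the definitions. The patient receives the Day 1 drugs and never receives BNT411.

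| Output | Population (SAP) | Patient included? |
|---|---|---|
| TEAE and SAE summaries, all-cause and per drug | Safety set (8.5, 8.5.2) | No |
| Exposure to each of the four drugs | Safety set (8.5.1) | No |
| Discontinuation of each drug; number of deaths | Safety set (8.2) | No |
| DLT summary | DLT evaluation set, a subset of the Safety set (7.1) | No |
| Counts and reasons for exclusion from each set | Enrolled set (8.2) | Yes |
| Listing of patients excluded from each set | Enrolled set (8.2) | Yes |
| AE, SAE and death listings | All data or all AEs (8.1, 8.5, 8.5.2, Appendix 1), but most listings on the Safety set (7.1) | Probably; 7.1 leaves some doubt |

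Two other rules do not handle this patient:

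- The as-treated rule in SAP 8.5 assigns the planned treatment if the planned dose was given at least once in Cycle 1, and otherwise the dose received on Cycle 1 Day 1. In Part 1B no BNT411 is scheduled on Day 1, so neither branch gives a BNT411 cohort.
- SAP 8.5.2 counts on-treatment deaths from the first BNT411 dose, whereas TEAEs are counted from the first dose of any trial treatment.

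**How likely is such a patient?** The documents give no rate of patients who never reach BNT411, so p = 1% to 5% is assumed, independently between patients. For n patients starting Day 1 treatment, P(at least one) = 1 − (1 − p)^n.

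SAP Appendix 3, Table 4, names two Part 1B cohorts (1.2 and 2.4 µg/kg). SAP 6 plans 3 to 6 DLT-evaluable patients per cohort, which gives 2 × 3 = 6 to 2 × 6 = 12 patients before any backfill.

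- n = 6: 1 − 0.99^6 = 5.9%; 1 − 0.95^6 = 26.5%.
- n = 12: 1 − 0.99^12 = 11.4%; 1 − 0.95^12 = 46.0%.
- n = 30, the upper limit of the plan: 1 − 0.99^30 = 26.0%; 1 − 0.95^30 = 78.5%.

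**What would one such patient change?** Suppose the patient has a serious Day 1 event, is replaced, and no one else has an event.

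- Cohort of 3: reported 0/3 = 0%; among all treated 1/4 = 25.0%.
- Cohort of 6: reported 0/6 = 0%; among all treated 1/7 = 14.3%.
- Twelve patients: reported 0/12 = 0%; among all treated 1/13 = 7.7%.

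If the patient left for a reason unrelated to toxicity and had no event, the shift is the other way: 1/6 = 16.7% reported against 1/7 = 14.3% among all treated.

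**The case against.** The strongest defence is that this is a first-in-human trial of BNT411. A patient given only the three approved drugs never received the combination under study, and a BNT411-exposed population is a defensible description that both documents state consistently. Two of the primary endpoints, dose reduction and discontinuation of BNT411, cannot occur in such a patient. The analyses are descriptive, and few patients are at stake. This justifies keeping a BNT411-exposed view, but it does not explain why the event window and the per-drug tables start on Day 1 while some recipients of the Day 1 drugs are left out.

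Three stronger readings are tempting, and the documents do not support them.

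- A reader might infer that missing the Day 2 infusion is enough to be dropped. The definition asks for one BNT411 dose at any time. BNT411 is also scheduled on Days 8 and 15 and in later cycles, and footnote 15 of Protocol Table 1-2 foresees delays. A patient dosed later enters the Safety set with all Day 1 events. Only those never dosed with BNT411 are lost.
- A reader might infer that the event disappears from the report. AEs are collected from consent (Protocol 8.7.1 and 10.3.3), and the committee that reviews safety sees cumulative AEs and SAEs (Protocol 9.6). The SAP also says in four places that all data, all safety data or all AEs are listed. The gap is in the summary tables, with some ambiguity over listings because SAP 7.1 bases most of them on the Safety set.
- A reader might count replacement as part of the harm. Replacing patients who cannot be evaluated for DLTs is ordinary in a 3+3 design. The difficulty is only that the patient also leaves the general safety summaries.

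**Conclusion.** The mismatch is real and stands in both documents. If the plan is followed exactly, a Part 1B patient treated on Day 1 who never receives BNT411 is excluded from the TEAE, SAE, death, exposure and discontinuation summaries. When the reason is a severe Day 1 event, the Part 1B rates are biased downward. The direction is not guaranteed for patients who leave for other reasons.

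The likely number is zero or a few. The chance of at least one is 6% to 27% for 6 patients and 11% to 46% for 12. This rests on the assumed 1% to 5%, which covers every reason for not reaching BNT411, so the chance of a downward bias is no higher than these figures. The 26% to 79% at 30 patients should not be read as the expected case, because 30 is a planning ceiling and SAP Table 4 names only two Part 1B cohorts. If no such patient exists, no result changes. The point is worth correcting because it touches the primary objective and the remedy is small.

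**What to change.** For Part 1B, choose one of two routes:

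- redefine the Safety set in SAP 7.1 and Protocol 9.3 as patients who received at least one dose of any trial treatment; or
- add an all-treated set with that definition to the SAP and use it for the all-causality TEAE, SAE, death and exposure tables and for the AE listings. SAP Appendix 1 already records one added analysis set, so this could be documented there.

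Under either route:

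- Show patients without BNT411 under their assigned cohort, with a flag.
- Amend the as-treated rule in SAP 8.5 so that these patients have a cohort.
- In SAP 8.5.2, start on-treatment deaths in Part 1B at the first dose of any trial treatment.
- Keep the BNT411-related TEAE and BNT411 exposure tables and the DLT, PK and PD sets restricted to patients given BNT411.
- Leave the replacement rules unchanged.

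The cost is one population definition and two consequential edits, with no new data. The drawback is that a few patients without BNT411 exposure may appear in the all-causality tables. The flag identifies them, and the restricted tables preserve the BNT411-exposed view.

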7.2 Protocol deviations

Protocol deviations are failures to adhere to the inclusion/exclusion criteria and protocol requirements and will be classified into important protocol deviations (IPDs) and non-important (NIPDs) protocol deviations.

The protocol deviation plan describes the classification process of the protocol deviations as “Key”/“Non-key”:

- The term “Key” deviation from protocol deviation plan is equivalent to IPDs in the SAP.
- The term “Non-key” deviation from protocol deviation plan is equivalent to NIPDs in the SAP.

IPDs will be identified by the trial team on an ongoing basis and will be finalized prior to database snapshot for the main analyses.

All protocol deviations will be presented in a listing. The IPDs will be summarized by cohort and total within each trial part for the Safety set.

7.3 Subgroups

There are no planned subgroup analyses.

8 STATISTICAL ANALYSES

8.1 General considerations

Unless otherwise specified, the details mentioned are for trial Parts 1A and 1B. The summaries will be presented as cohort and total within trial part (Part 1A and Part 1B). The presentation of data for Part 2 will be included in a SAP amendment.

No formal statistical comparisons between cohorts/trial parts will be performed.

Continuous variables will be summarized by cohort and total (as specified) using the following descriptive statistics: number of patients with non-missing data (n), mean, standard deviation (SD), median, minimum (min) and maximum (max).

Categorical variables will be summarized by cohort and total (as specified) presenting absolute and relative frequencies (n and %) of patients in each category and the number of patients with missing data (missing category will be presented if there is one or more missing value). Percentages will be calculated based on the number of patients with non-missing data (n) in the particular analysis set as the denominator. The text (N=xx) in the tables denotes the number of patients in the analysis set within each cohort. For event-driven occurrence data (e.g., adverse event, concomitant medication, etc.) the percentages will be based on the number of patients in the analysis set (N). For reported visit data (e.g., gender, [Eastern Cooperative Oncology Group] ECOG performance status, etc.) the percentages will be based on the number of patients with non-missing values (n).

All data collected during the trial will be listed, the trial day will be presented as appropriate. The data will be sorted by trial part (Part 1A, Part 1B) cohort, patient number cycle (if applicable) and date of assessment (if applicable).

All analyses will be conducted using SAS® version 9.4 or higher.

Baseline is defined as last available value prior to first dose of any trial treatment (i.e., for Part 1A BNT411 and for Part 1B BNT411 or atezolizumab or carboplatin or etoposide).

Generally, if there are multiple assessments available for a particular day, the assessment that is closest to the day (and time if collected) of the first dose of any trial treatment (i.e., BNT411 or atezolizumab or carboplatin or etoposide) will be used as the baseline value in the summary/analyses.

Multiple values at post-baseline visits: if there are multiple post-baseline assessments available within a visit/day, the earliest value and corresponding date/time will be considered.

Change from baseline: Unless and otherwise specified, will be calculated as follows:

Change from baseline = post-baseline assessment value – baseline assessment value.

If either the baseline or post-baseline assessment value is missing, the change from baseline is set to missing as well.

For the derivations of PK and PD data, see Section [8.6.1](#) and [8.6.2](#).

Duration (Other than “Trial Treatment Duration” defined in Section [8.5.1](#)) will be calculated as follows:

- Duration = last observation date – first observation date + 1.

For conversion of days to months or years the following rules will be applied:

- 1 month = 30.4375 days
- 1 year = 365.25 days

Trial Day and Treatment Day will be calculated for each trial part (1A and 1B) as follows:

- Trial day:
 - If assessment date < treatment start date then trial day = assessment date – treatment start date
 - If assessment date >= treatment start date then trial day = assessment date – treatment start date + 1
- Treatment Day = treatment date – date of first dose of BNT411 +1

That is, trial day 1 indicates the date of treatment initiation.

For BNT411, it is Cycle 1 Day 1 of Part 1A and Cycle 1 Day 2 of Part 1B. For atezolizumab, carboplatin and etoposide it is Cycle 1 Day 1 of Part 1B.

All trial data will be presented as collected in the eCRF/visit assigned in external data. No windowing of data for the purposes of assigning to a visit will occur.

Unscheduled assessments will be listed only and not included in summaries/analysis.

Handling missing data:

For the purposes of assigning treatment-emergent flag for adverse events (AEs), partial or missing AE dates will be handled as follows (trial treatment date is the earliest date of BNT411 in Part 1A and earliest date of atezolizumab, BNT411, carboplatin and etoposide in Part 1B).

- If the day of the month is missing, the onset day will be set to the first day of the month unless it is the same month and year as trial treatment. In this case, in order to conservatively report the event as treatment-emergent, the onset date will be assumed to be the first date of trial treatment.

- If the onset day and month are both missing, the day and month will be assumed to be January 1, unless the event occurred in the same year as the trial treatment. In this case, the event onset will be coded to the day and month of treatment in order to conservatively report the event as treatment-emergent.
- A completely missing onset date will be assumed to be the first day of trial treatment.
- If an AE has a partial start date that is in the same month/year as the first dose of trial treatment, then the AE will be reported as treatment-emergent.

Partial anti-cancer therapy start dates will be handled as follows:

- If the start of subsequent anti-cancer therapy date is missing, this will be imputed to the date of the end of treatment (EOT) visit.
- Missing day, month/year present: If the month/year is the same as the month/year of EOT Visit date, then impute missing start dates with EOT Visit date. Otherwise, for dates corresponding to a start date, impute with the first day of the month.
- Missing month/day, year present: If the year is the same as the year of EOT Visit date, then impute missing start dates with EOT Visit date. Otherwise, for dates corresponding to a start date, impute with the first day of the year.
- If the EOT Visit date is missing, the date of last treatment will be used for imputation.

For the purposes of assigning prior or concomitant flag for medications, partial or missing medication dates will be handled as follows:

- If end day is missing and month/year are non-missing, then day is the minimum of treatment end date and the last day of the month.
- If end day/month are missing and year is non-missing, then day is the minimum of treatment end date and the end of the year (31DECYYYY).
- If imputed end date is less than the start date, use the start date as the imputed end date.

Start dates:

- If the start date year is missing, the start date is set to one day prior to treatment start date.
- If the start date year is less than the treatment start date year, then:
 - If the month is missing, the start date is assumed to be mid-year point (01JULYYYY).
 - Else if the month is not missing, the start date is assumed to be mid-month point (15MONYYYY).
- If the start date year value is greater than the treatment start date year, then:
 - If the month is missing, the start date is assumed to be the year start point (01JANYYYY).

- Else if the month is not missing, the start date is assumed to be the month start point (01MONYYYY).
- If the start date year value is equal to the treatment start date year value:
 - If the month is missing or the month is equal to the treatment start date month, then the start date is assumed to be one day prior to the treatment start date.
 - Else if the month is less than the treatment start date month, the start date is assumed to be the mid-month point (15MONYYYY).
 - Else if the month is greater than the treatment start date month, the start date is assumed to be the month start point (01MONYYYY).

If complete end date is available and the start date assumed from the steps above is greater than the end date, then the assumed start date should be set to the end date.

Missing data, other than that described for AEs/CMs/ above will not be imputed.

Listings will present all data as reported (i.e., without imputations).

For analysis of PK and PD data:

- The actual date collected will be used. If the date is not available, the value will be considered as missing.
- The actual time of sample collection will be used. If the time is not available, the value will, at the discretion of trial pharmacokinetics/pharmacodynamics analyst (in consultation with BioNTech), be considered as missing or imputed to be the nominal sampling time.

